10.2 Screening and Eligibility Assessment

All patients admitted to a participating site ICU during the study period meeting the screening inclusion criteria will be entered into a screening log and followed daily until they satisfy all inclusion criteria, are enrolled and randomized, or meet one of the exclusion criteria and exit the screening/enrolment process. A participant will be ineligible for participation in this study and will be counted as a "screen failure" if he or she satisfies any one or more of the exclusion criteria. A staged enrolment process will be used to identify patients eligible to be enrolled and randomized in the study. The five stages of enrolment are:

A. Screening Criteria**B. Consenting Criteria and Obtaining Consent****C. Pressure Support Trial Criteria and the Pressure Support Trial****D. Weaning Criteria and the ZERO CPAP Trial and the Spontaneous Breathing Trial (SBT)****E. Randomization Criteria**

See section 7.0: Participant Identification and Appendix B for additional information on screening and eligibility assessment.

Informed consent will be administered prior to any study procedures and will be compliant with local institutional/REB requirements. See sec. 15.3 for additional information on consent.

10.3 Randomization & Blinding**10.3.1 Randomization**

Participants will be randomized once eligibility is determined, by having satisfied all of the inclusion criteria and none of the exclusion criteria, have passed the Pressure Support Trial and either not meeting Weaning Criteria or failing the ZERO CPAP Trial or failing the SBT. Each participant in this study will be randomized to either PSV or PAV+ in a 1:1 ratio in Medidata RAVE.

Participant allocation to procedure group will be via variable block randomization with varying block sizes and stratified by site to minimize the likelihood of predicting the next procedure assignment. Randomization will be attained using computer generation sequence methodology, ensuring that the randomization methodology and the generated allocation sequence are concealed from the investigator and participants.

10.3.2 Blinding

Neither the clinical team nor the study investigators will be blind to the study intervention. The study statistician will be blind to the study arm.

10.4 Baseline Assessment

A Pre-Randomization assessment will be recorded immediately prior to implementing PSV or PAV+ to provide a baseline measure for evaluation. The Pre-Randomization assessment will include:

- Ventilator settings and most recent arterial blood gas (ABG) results prior to the Pressure Support Test (PST)
- Ventilator settings used for the PST, and respiratory parameters, vital signs, and arterial blood gas results at the end of the PST

A Randomization form will be completed to document:

- Weaning Criteria
- ZERO CPAP Trial result (RR and Vt or RSBI)
- SBT result: failure criteria
- Randomization assignment

10.5 Administration of Intervention

Switching ventilator mode to PSV or PAV+ with adjustment of the settings according to the assigned PSV or PAV+ Ventilation Strategy will indicate administering the intervention. The intervention (the PSV or PAV+ Ventilation Strategy) is administered continuously from time of randomization until study completion (study completion occurs at time of successful extubation/successful termination of invasive MV, successful ICU discharge, hospital discharge, death or 90 days post randomization, whichever comes first).

10.6 Follow up assessments and Final Study Visit

A Post-Randomization assessment will be recorded 1 hour post-randomization and will include:

- Make and model of ventilator, ventilator settings, respiratory parameters and vital signs

Day of randomization is considered Day 1, until 0700 a.m. Each subsequent study day is from 0700 a.m. to 0700 a.m. Daily follow-up “snapshot” assessments are completed daily (or on selected days) between 0800 a.m. -1200 p.m. and will include daily assessment for Criteria to Initiate Weaning and results of Pre-SBT readiness assessments and SBTs.

Daily follow-up “cumulative” assessments are completed based on the 0700 – 0700 hrs time frame and will include data on co-interventions administered in each 24 hour interval.

Event-based assessments are conducted at the time of the following events: extubation, use of NIV post-extubation, reintubation, tracheostomy, protocol deviation, or serious adverse events.

An outcome assessment will be recorded to document time of successful extubation, time of successful ICU discharge, time of hospital discharge, or death.

A final study visit will occur on Day 90 to document vital status and outcome assessment if not previously completed.

10.7 Protocol Amendments and Deviations

Investigators must read, understand and follow the study protocol.

Amendments are changes to the protocol (or protocol procedures) that are planned and that are approved by the REB prior to implementation. Changes to the protocol shall only be made by the EC in the form of protocol amendments. The CC is responsible for the distribution of any protocol amendments to site Investigators. Site Investigators are responsible for the distribution of an amendment to all staff involved in the study and for obtaining approval for the amendment from the local REB as required by local institutional guidelines.

Deviations differ from amendments in that they generally apply to a single occurrence or participant, and are not intended at the time to modify the entire protocol. Examples of protocol deviations that must be recorded and reported to the CC and may be reported to the REB per local institutional requirements include the following:

- Implementation of additional procedures for monitoring participants, beyond the standard of care;
- Suspension of enrollment of new participants;
- Suspension of research procedures in currently enrolled participants

In the event that a patient is randomized in error (e.g. incorrect eligibility assessment) the site should notify the CC immediately, and make a note in the patient’s source documents. Patients randomized in error will be withdrawn from the study. The site will be required to document and implement a preventative action plan to avoid future errors.

If an unanticipated deviation or divergence from the approved research protocol, consent document(s) or study addenda **jeopardizes participants, study efficacy or data integrity**, it must be promptly reported to the CC and

may be reported to the local REB per local institutional requirements, if it has not otherwise been reported through an amendment to the protocol or consent form. Specific examples of reportable deviations (i.e., if they place participants at a greater risk) include the following:

- Informed consent improperly obtained or not obtained;
- Participant enrolment without meeting the eligibility criteria and without prior sponsor approval;
- Eligibility Waiver: participant enrolment without the eligibility criteria with prior sponsor approval;
- Assigned ventilation strategy not administered per protocol with increased risk of harm to participant;
- Major, non-emergent deviations without prior approval;
- Emergency deviations to the research protocol initiated by the investigator prior to obtaining REB approval to (e.g., eliminate apparent immediate hazards to participants).

Emergency deviations to the research protocol (e.g. to eliminate apparent immediate hazards to participants) will also be reported to funding agencies according to contract stipulations, no later than five (5) working days after the emergency situation occurred. Protocol Deviations that lead to an SAE must be reported according to guidelines set forth in section 11.3.

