12.2 Statistical Methods Analysis

Analysis will follow the intention-to-treat principle. Baseline data will be analyzed descriptively (e.g. mean and standard deviation, median and interquartile range, counts and percentages as appropriate). Time to extubation will be summarized by cumulative incidence curves with death treated as a competing risk and compared between groups with the Gray test. The treatment effect will be expressed as a hazard ratio with 95% confidence interval from a multistate generalization of the Cox model. Additionally, a cause-specific Cox model where death is treated as a censoring event will be fit for comparison. Patients with missing outcome data will be censored at last contact. The secondary outcomes of ventilator-free days will be compared between the groups by means of a Wilcoxon test. The treatment effect will be expressed as the difference in median ventilator free days along with a 95% confidence interval obtained by bootstrap methods. The time-to-event outcomes ICU discharge and hospital discharge present the same special challenge as the primary outcome because death is a competing risk. Furthermore, "survivor-only" analyses are an improper subgroup which further complicates interpretation. To mitigate these problems, cumulative incidence curves will be constructed that provide estimates of the outcome of interest, accounting for death. Cause-specific treatment effects will be given as hazard ratios with 95% confidence intervals from Cox models. Time-to-death will be analyzed using standard methods for survival data (Kaplan-Meier curve, log-rank test) and the treatment effect will be expressed as a hazard ratio with 95% confidence interval. Four of the secondary outcomes describe weaning difficulties in various ways. These also suffer from the competing risk of death and other improper subgroup issues. These outcomes will be looked at primarily from a descriptive perspective. The outcome, "requiring A/C" will be compared by a chi-square test (or Fisher's Exact Test) and treatment difference will be expressed as an odds ratio with 95% confidence interval.

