3.2 Handling of Incomplete Data

It is important to realize that the problem of incomplete data is distinct from ITT. The ITT philosophy is to attribute the available patient data to the group they were randomized to, irrespective of compliance to randomization. However, it is not possible to analyze data that you do not have. Therefore, we will begin with the complete case analysis. However, this analysis can be biased, although if missing data is minimal, less than 5% say, bias will be minimal and conclusions will not be affected by more sophisticated approaches.

There is controversy regarding the appropriateness of imputing outcome data in clinical trials. Therefore, even if loss to follow-up (i.e. missing outcome) exceeds 5% no imputation methods will be employed for post-randomization outcomes. The main value of imputation techniques is to enable an analysis to use all complete data. Some unpublished simulations developed by the statistician demonstrate that if the outcome is the only thing missing, even if missing at random, multiple imputation has virtually no effect on bias or precision. Furthermore, post-randomization outcome data is frequently not missing at random and other simulations conducted by the statistician show multiple imputation may not correct the bias incurred by data not missing not at random. Also note that since the primary analysis is a time-to-event analysis, no subjects are dropped from the analysis, they are simply censored if necessary. Multiple imputation may be employed to handle missing covariate data in secondary, adjusted analyses.

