4.6.1 Intention To Treat Sample

All analyses will use the intention to treat sample. The intention to treat sample will be comprised of all randomized patients who started the study intervention, irrespective of compliance to their randomized group. Patients will contribute outcome data to the analysis based on the randomized group.

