4.6.2 Per Protocol Sample

The per-protocol sample will include only those randomized patients who stayed on the study protocol until successful liberation from IMV, 90 days, or death, whichever came first. The per-protocol sample will exclude subjects who were withdrawn from the study, or spent more than 48 hours in a non-protocolized mode of ventilation duringthe first 21 days (neither PAV, nor PSV, nor CPAP, nor AC). Note that use of assist-control mode in either volume or pressure control was allowed per protocol in each arm of the study. The per-protocol sample will also exclude patients who were transferred to another centre or ward prior to completing the study protocol, with the exception of patients who were transferred for palliation and died within 7 days of transfer; such patients will be considered to have completed the study protocol, and will be included in the per protocol sample.

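### The rule that patients randomized in error are withdrawn from the study conflicts with intention to treat and is reconciled nowhere; it risks lost follow-up and a modest bias in the liberation hazard ratio.

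*Protocol*

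**What the plan says.** Protocol 10.7 sets the rule. The trigger is a report from the site: "In the event that a patient is randomized in error (e.g. incorrect eligibility assessment) the site should notify the CC immediately". The consequence follows: "Patients randomized in error will be withdrawn from the study". The section does not say whether follow-up stops, whether data already collected are kept, or whether the patient is analysed. Under Protocol 10.3.2 neither the clinical team nor the investigators are blind to the arm.

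On analysis, Protocol 12.2 says "Analysis will follow the intention-to-treat principle" and adds "Patients with missing outcome data will be censored at last contact". SAP 4.6 repeats the censoring rule. SAP 4.6.1 defines the main sample: "The intention to treat sample will be comprised of all randomized patients who started the study intervention, irrespective of compliance to their randomized group". SAP 4.6.2 deals with withdrawal only for the secondary sample: "The per-protocol sample will exclude subjects who were withdrawn from the study". SAP 4.6.3 bases safety on all randomized patients, whereas Protocol 6.4 bases it on those randomized who received PAV+ or PSV per protocol. The SAP never mentions patients randomized in error.

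On participation, Protocol 9.2 and 10.5 list the events that end it: successful extubation or its tracheostomy equivalent, successful ICU discharge, live hospital discharge, death, or day 90. Withdrawal for a randomization error is not among them.

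**The concern.** A patient's eligibility is a baseline fact, but its discovery comes after allocation. Under 10.7 the discovery is made by people who know the arm and may know the early course. If errors are found or reported more readily in one arm, and the affected patients differ in prognosis, removing them or cutting short their follow-up unbalances the groups that randomization made comparable. Outcomes that were never collected cannot be recovered by analysis.

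Errors are plausible. Protocol 7.3 is a five-stage chain that includes a forecast of ventilation need (B6), a limit of 24 consecutive hours on partial support (B9) and an exclusion for a passed breathing trial (E3). Errors on B9 or E3 may pick out patients close to liberation. That is inference, since the documents report no error rate.

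The point at which treatment starts could also differ by arm. A patient who passes the pressure support trial may stay on pressure support (7.3), and the PSV arm may use any suitable ventilator (8.2.1). PAV+ needs one of two named ventilators and a change of mode (8.1.1). An error found soon after allocation might therefore more often precede the start of treatment in the PAV+ arm. This too is inference.

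**Working it through.** **What happens to the patient under the text**

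1. *Started the assigned mode, then withdrawn.* In the intention-to-treat sample by SAP 4.6.1. If withdrawal ends follow-up, censored at last contact, possibly informatively.
2. *Withdrawn before starting.* Outside the intention-to-treat sample by SAP 4.6.1, and outside the safety population of Protocol 6.4 though inside that of SAP 4.6.3.

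The text suggests, without stating, that follow-up ends. SAP 4.4 separates leaving the intervention from leaving data collection, and 10.7 names the study, not the intervention. For patients who revoke authorization, Protocol 9.3 asks sites to seek permission to collect vital status; 10.7 asks nothing similar.

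**The plan's own figures (Protocol 12.1)**

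- Inputs: hazard ratio 1.30, two-sided 5%, 80% power, PSV median 7.70 days, 456 events, 529 patients, 5% loss.
- Events (Schoenfeld): 4 × (1.960 + 0.842)² / (ln 1.30)² = 456.1. The plan states 456, which gives 79.99% power.
- PAV+ median: 7.70 / 1.30 = 5.92 days.
- Randomized: 529 / 0.95 = 556.8, so 557, or 558 for equal arms.

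The plan's figures are reproduced.

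**Bias in the liberation hazard ratio**

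- PSV liberation hazard: λ = ln 2 / 7.70 = 0.0900 per day. PAV+: λ times the true ratio.
- Death hazard m, constant and equal in both arms, solved from 456/529 = 0.862 = ½[λ/(λ+m) + 1.3λ/(1.3λ+m)], giving m = 0.0163 per day.
- Assumed: a share e = 2% or 5% of *each* arm is randomized in error, with liberation hazard h = 0.5 or 2 times that of other patients.
- In arm a: at risk R(t) = (1−e)exp[−(λₐ+m)t] + e·k(t)·exp[−(hλₐ+m)t]. The event rate E(t) is the same sum with terms multiplied by λₐ and hλₐ. For withdrawn patients k = 0 throughout (removed), or k = 1 to day 1 and 0 afterwards (censored). Otherwise k = 1.
- Solve ∫[E₁ − (E₀+E₁)·R₁e^β/(R₀+R₁e^β)]dt = 0 over 0 to 90 days. The hazard ratio is e^β.

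This is the large-sample cause-specific Cox estimate (the secondary analysis in SAP 6.1.2), not the planned multistate model.

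True hazard ratio 1.00; cells show removed / censored at day 1:

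| e, h | Withdrawn in PAV+ only | Withdrawn in PSV only | Both arms |
|---|---|---|---|
| 2%, 0.5 | 1.017 / 1.016 | 0.983 / 0.984 | 1.000 |
| 2%, 2 | 0.989 / 0.991 | 1.011 / 1.009 | 1.000 |
| 5%, 0.5 | 1.043 / 1.040 | 0.959 / 0.962 | 1.000 |
| 5%, 2 | 0.973 / 0.978 | 1.028 / 1.023 | 1.000 |

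Early censoring is thus nearly as harmful as removal. With a true ratio of 1.30, one-arm removal gives 1.276 to 1.321 (2%) or 1.242 to 1.351 (5%). Withdrawal in both arms gives 1.300, and keeping everyone gives 1.291 to 1.298.

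**Scale**

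With 456 events the standard error of the log hazard ratio is about 2/√456 = 0.094. The largest shifts are ln 1.017 / 0.094 = 0.18 and ln 1.043 / 0.094 = 0.45 standard errors. The two-sided error rate would be about 1−Φ(1.78)+Φ(−2.14) = 5.4% and 1−Φ(1.51)+Φ(−2.41) = 7.3%.

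**Power**

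At 1.30, from 558 randomized and 456/529 events per patient: 82.0% with no loss, 81.3% with 2% lost, 80.1% with 5% and 77.9% with 10%.

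**The case against.** The strongest reply is that 10.7 is about conduct and the SAP governs analysis. SAP 4.6.1 has no ineligibility exclusion. SAP 3.2 says the time-to-event analysis drops nobody and censors where needed, and describes the principle thus: "The ITT philosophy is to attribute the available patient data to the group they were randomized to, irrespective of compliance to randomization". Withdrawn subjects are removed only from the per-protocol sample, and SAP 4.4 plans to report withdrawals and incomplete follow-up with reasons. This stands against one tempting inference, that the plan excludes ineligible patients from the primary analysis: the documents do not say so. It does not answer early censoring, or the loss of patients withdrawn before starting.

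Three other stronger readings also fail.

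- *Waiver patients stay while mistaken entries go.* Protocol 10.7 lists "Eligibility Waiver: participant enrolment without the eligibility criteria with prior sponsor approval" only as an example of a reportable deviation, beside ineligible enrolment without approval. Nothing says what happens to waiver patients afterwards.
- *PAV+ attracts closer eligibility review.* No passage supports this. Many criteria are numeric and recorded at baseline (Protocol 10.4), and prompt notification is required, which limits late reclassification without ruling it out.
- *The bias is large.* Withdrawing 14 of 279 patients from the slowest quarter of one arm gives a hazard ratio near 1.08 and an error rate of about 13% to 14%. But that picks patients by an event time not yet known at an early withdrawal, in one arm and one direction. A half-and-half mix of slow and fast patients in one arm gave 1.015 at the same number, with error rates across the mixed scenarios no higher than 6.1%.

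**Conclusion.** The concern holds in limited form. Protocol 10.7 contains a mandatory, site-triggered, unblinded withdrawal rule that conflicts with the intention-to-treat principle in 12.2 and is not reconciled with Protocol 9.2 or SAP 4.6. Followed as written, it may end collection of outcome and safety data, with possibly informative censoring, and it takes patients withdrawn before starting out of the intention-to-treat sample.

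The size is modest: a shift of about 1% to 2% in the hazard ratio at a 2% error rate and 2% to 4% at 5%, and only if withdrawal differs by arm and prognosis differs. Under the null, equal withdrawal causes no bias. The error rates, the hazard multiples of 0.5 and 2, and one-arm withdrawal are all assumptions. The sample size is not in question: the 5% allowance covers losses of this order, and Protocol 12.1 continues enrolment until the required events are reached. The case for acting is that the fault lies in the rule itself and is cheap to remove.

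**What to change.** Replace the sentence in Protocol 10.7 with: *Patients randomized in error remain in study follow-up, subject to consent; outcome, SAE and day-90 data are collected, and they are analysed in their randomized arm.* Record each error as a protocol deviation, and report numbers, reasons and timing by arm.

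Add a matching line to SAP 4.6, so that the intention-to-treat sample expressly includes these patients, whether or not they had started the assigned mode. Any exclusion should be confined to a sensitivity analysis, decided by assessors blind to arm and outcome and from pre-randomization data only.

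Whether the assigned mode continues is a clinical matter on which this point takes no position. Protocol 9.2, 10.5 and 10.7 need to be reconciled on what ends study participation. If patients have already been withdrawn under the rule, state how many in each arm, when, and what follow-up exists.

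The cost is a sentence in the protocol, a line in the SAP and follow-up of a few patients. Keeping them dilutes the estimate slightly: under the assumed rates a hazard ratio of 1.30 becomes 1.291 to 1.298. The design figures of 456 events, 529 patients and 558 randomized do not change.

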11.0 Safety Assessments

11.1 General Comments

The ventilation algorithms and study protocol provide a variety of measures to ensure the safety of enrolled patients, including instructions to use assist/control ventilation in case of clinical instability, or in the event that respiratory distress or impaired gas exchange does not resolve with optimizing ventilator settings on PAV+ or PSV. Based on the 2 pilot studies performed by the co-primary investigators, we anticipate no increase in risk to participants in this trial. Nonetheless, the target population for this trial is critically ill patients with a high baseline risk of complications and death. We expect that some patients may die during the course of their enrolment in the study. If the patient expires the site investigator is required to complete a SAE assessment in their source documents. A death due to a decision to withdraw life support, or a decision to not re-intubate post extubation, or a change in the goals of care, does not constitute a serious adverse event and does not need to be reported as such. We are interested in reviewing Serious Adverse Events that *may* be related to the study interventions, rather than adverse events that occurred due to the underlying critical illness. An independent Data Safety Monitoring Board (DSMB) will review each Serious Adverse Event for which a possible, probable, or definite relationship to the study intervention exists.

Notwithstanding the safety measures provided within the ventilation algorithm, in the event of an emergency situation, the site PI and/or attending physician will ensure that best medical judgment is used to protect the life or well-being of the participant, which may include deviations from the Protocol. The safety and welfare of participants in the study takes absolute precedence over the evaluation goals and objectives of the study, in any emergency situation. Reporting of protocol deviations is described in section 10.7, and reporting of serious adverse events is described below in section 11.3.

A Serious Adverse Event (SAE) in the PROMIZING Study is defined as:

Any adverse event that results in 1 of the following:

- Results in unanticipated/non-palliative death
- Life-threatening
- Results in persistent or significant disability/incapacity:

- Requires medical or surgical intervention to prevent one of the above outcomes

Examples of reportable SAEs:

Criteria for SAE	Definition
Results in unanticipated/ non-palliative death	An adverse event which directly results in the patient's death, excluding one-way extubations, withdrawal of life support, or expected deaths occurring in patients who have been made palliative (eg. Cardiac arrest with unsuccessful attempt at resuscitation)
Life-threatening	An event in which the subject was at risk of death at the time of the event (eg. respiratory or circulatory arrest with return of spontaneous circulation)
Results in persistent or significant disability/incapacity	An event which results in significant, persistent disability AFTER the event has resolved/ been treated (eg. hypotension leading to stroke with resulting hemiplegia)
Requires medical or surgical intervention to prevent one of the above outcomes	An important medical event that may not result in death or be life-threatening but may jeopardize the subject and requires medical or surgical intervention to prevent one of the above outcomes, based on appropriate medical judgment. (e.g. a patient has an episode of major agitation leading to self-extubation, requiring re-intubation)

